11.5. Adverse and Serious Adverse Events

EASR will also be assessed at four time points from the start of radiotherapy through 4 weeks of the post radiotherapy follow-up period. The RTOG scale will be used for classification of EASRs related to the skin. The Investigator is responsible for the detection and documentation of events meeting the criteria and definition of a non-serious AE or SAE as provided in this protocol. During the study, as defined from the time of informed consent until completion of study-related procedures, the Investigator or site staff will be responsible for detecting and following AEs and SAEs, as detailed in this section of the protocol. Adverse events will be reported by the subject (or, when appropriate, by a caregiver, surrogate, or the subject's legally acceptable representative). We will also estimate the incidence of EASR of any grade, and for grades 2 and higher. At each time point we will estimate the proportion of women who have RT-induced EASR present and also calculate a 95% confidence interval around this estimate.

11.5.1. Definitions

11.5.1.1. Adverse Event (AE)

An adverse event (AE) is defined as any unfavorable or unintended change in body structure, body function, laboratory result (e.g., chemistry, ECG), or worsening of a pre-existing condition associated temporally with the use of the test product, whether or not considered related to the test product.

11.5.1.2. Serious Adverse Event (SAE)

A serious adverse event (SAE) is any untoward medical occurrence that occurs irrespective of study treatment assignment, if it satisfies any of these criteria: results in death; is life-threatening; requires inpatient hospitalization or prolongs existing hospitalization; results in persistent or significant disability or incapacity or substantial disruption of the ability to conduct normal life functions; or if the event results in a congenital anomaly or birth defect. All SAEs should be reported to the study sponsor within 24 hours of the investigator being aware of the event.

11.5.2. Adverse Event Reporting

Subjects will be encouraged to spontaneously report any changes in baseline health from the time the subject enters the study through study completion. Study staff also will inquire about AEs on each visit while the subject is in the research center. All AEs/SAEs will be recorded in the source document and the case report form (CRF).

Version: 00

Effective Date: 03-01-2018

11.6. Relationship to Study Device

11.6.1. Assessment of Causality

The Investigator is obligated to assess the relationship between study device and the occurrence of each AE/SAE. The Investigator will use clinical judgment to determine the relationship. Alternative causes, such as natural history of the underlying diseases, concomitant therapy, other risk factors, and the temporal relationship of the event to the study device will be considered and investigated.

The Investigator will assess causality based on the following definitions:

- **Not Related** (the AE was more likely explained by causes other than the study treatment).
- **Related** (the study treatment and AE were closely related in time and the AE may be explained by exposure to study product: e.g., known adverse effect or recurrence on rechallenge).

11.7. Recording Adverse Events

When an AE occurs, it is the responsibility of the Investigator to review all documentation (e.g., medical progress notes, laboratory, and diagnostics reports) relative to the event. The Investigator will then record all relevant information regarding an AE in the CRF.

The Investigator will attempt to establish a diagnosis of the AE based on signs, symptoms, and/or other clinical information. In such cases, the diagnosis should be documented as the AE/SAE and not the individual signs/symptoms.

11.7.1. Eliciting Adverse Event Reports

At each visit, subjects will be asked about AEs by means of a non-leading question, such as "how have you been since your last visit?" or "how has the treatment been?" In this way, possibly milder, but clinically important, side effects of the study device can be detected. SAEs will be reported promptly to KeraNetics as described in the following table once the Investigator determines that the event meets the protocol definition of a SAE.

11.7.2. Assessment of Intensity

The Investigator will make an assessment of intensity for each AE/SAE reported during the study. The assessment will be based on the Investigator's clinical judgment. The intensity of each AE/SAE recorded in the CRF should be assigned to one of the following categories:

- **Mild:** An event that is easily tolerated by the subject, causing minimal discomfort and not interfering with everyday activities.
- **Moderate:** An event that is sufficiently discomforting to interfere with normal everyday activities.
- Severe: An event that prevents normal everyday activities.

Version: 00

Effective Date:

03-01-2018

An AE that is assessed as severe should not be confused with a SAE. Severity is a category utilized for rating the intensity of an event; both AEs and SAEs can be assessed as severe.

11.8. Reporting Adverse Events

An unexpected event is one that is not consistent with the subject's past medical history and is not evident from previous clinical experience with the test product or reasonably anticipated from information known about the test product. Events that are deemed serious, related, and unexpected involve special handling and reporting requirements to the IRB. All SAEs will be followed until stabilization or improvement.

11.8.1. SAE Reporting Procedures

Once an Investigator becomes aware that a SAE has occurred in a study subject, she/he will report the information as thoroughly as possible with all available details of the event to the Sponsors within 24 hours. If the Investigator does not have all information regarding an SAE, he/she will not wait to receive additional information before notifying Sponsor of the event. The information regarding the event will be updated when additional information is received. The Investigator will always provide an assessment of causality at the time of the initial event report as described in Section 11.6.1. An email is the preferred method to transmit this information regarding a SAE to the project contact for SAE receipt. In rare circumstances and in the absence of email equipment, notification by telephone is acceptable, with a copy of the event details sent by overnight mail. Initial notification via the telephone does not replace the need for the Investigator to complete the SAE report via email within 24 hours.

11.8.1.1. Regulatory Reporting Requirements for SAEs

Sponsor has a legal responsibility to notify, as appropriate, both the local regulatory authority and other regulatory agencies about the safety of a product under clinical investigation. Prompt notification of SAEs by the Investigator to the appropriate project contact for SAE receipt is essential so that legal obligations and ethical responsibilities towards the safety of other subjects are met.

11.8.2. Reporting Safety Information to the IRB

The Investigator, or responsible person according to local requirements, will comply with the applicable local regulatory requirements related to the reporting of SAEs to the Institutional Review Board (IRB) / Institutional Ethics Committee (IEC).

11.8.3. Protocol Deviations Due to an Emergency or Adverse Event

Any subject experiencing an emergency or adverse event requiring immediate medical attention will receive appropriate medical management by medical staff at the site and at other clinical sites as indicated. These events will be reported to Sponsor as soon as possible. If the medical management results in departure from the study protocol, the Sponsor will be responsible for granting permission for the subject to continue in the trial if the subject is able to return to study protocol adherence in a timely fashion. If the subject cannot return to the study protocol in a timely fashion, then the subject will be discontinued from the study.

KeraNetics, LLC. CONFIDENTIAL Page 23

Version: 00

Effective Date:

03-01-2018

11.9. Follow-up of Adverse Events

After the initial AE/SAE report, the Investigator is required to proactively follow each subject and provide further information to Sponsor on the subject's condition. All AEs and SAEs documented at a previous visit/contact and designated as ongoing, will be reviewed at subsequent visits/contacts.

All AEs and SAEs will be followed until resolution, until the condition stabilizes, until the event is otherwise explained, or until the subject is lost to follow-up. Once resolved, the appropriate CRF entries will be updated.

12. STATISTICS

12.1. Description of Statistical Methods

Descriptive statistics will calculated and used to inform additional device development and to inform a power calculation for a follow on study, if required. The completion rate will be used as a measure of feasibility, with participants with an average of 10 or more applications per week being classified as compliant. A 95% confidence interval will be calculated around the estimate of compliance. After summary statistics are calculated by group, a t-test will be used to compare the two treatment groups for the effectiveness outcomes of DLQI score and RTOG score. A Fisher's exact test will be used to compare skin appearance issues between the groups. The counts for each type of adverse event will be summarized by grade and treatment group. For the KeraStat treatment group, the mean coverage will be calculated per square centimeter.

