1. SYNOPSIS

Name of Company:Name of Product:Type of Study:KeraNetics, LLCKeraStat® CreamClinical Proof of Concept

Title of Study: Pilot Study: KeraStat® Cream for Radiation Dermatitis

Investigator(s): [name], PhD; [name], PhD

Study Period: Estimated screening expected to start March 2018; Expected completion September 2018

Phase of Development: Design & Development (Phase 3 of Design Control)

Objective(s):

Primary:

- To assess feasibility (compliance of use)
- Collect data for designing a larger future trial evaluating KeraStat Cream

Secondary:

- To assess the safety and tolerability of KeraStat Cream in subjects at risk of radiation dermatitis
- To assess the effectiveness of KeraStat Cream compared to standard of care to manage the symptoms of radiation dermatitis in subjects being treated with radiation therapy
- To estimate amount of KeraStat Cream used per patient and coverage on skin

Methodology: This is a randomized, open label study.

Number of Subjects:

Sufficient subjects will be screened and enrolled such that 24 total subjects, 12 subjects per treatment group, will complete the study through the Follow-Up Visit. With 12 participants in each treatment group, we will be able to calculate a 95% confidence interval around the compliance rate in each group with a maximum margin of error of 0.283. Comparisons between groups for effectiveness will have 80 percent power to detect a difference of 1.2 standard deviations. Results of the current study are intended to provide descriptive endpoint data to inform the design of a future clinical evaluation of product effectiveness.

Study Overview:

Study Periods:

The length of study participation for a subject is about 8-12 weeks, depending on the length of radiation treatment. The study will extend 4-6 weeks beyond the end of radiation therapy. The study will begin with a Screening Visit during treatment planning followed by weekly assessments during radiation therapy, and a follow up visit 4-6 weeks after completion of therapy. There is a total of 5-7 visits.

Study Assessments:

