At the Screening/Baseline Visit (Visit 1, Week 0), following informed consent, initial eligibility will be verified per the inclusion/exclusion criteria and demographics and brief medical history will be collected. Subjects will be randomized to receive standard of care or KeraStat Cream. A physical exam and photograph of the area to be irradiated will be obtained, and subjects will complete the Dermatology Life Quality Index.

During the course of radiation therapy (4-6 weeks) and for the duration of the post RT treatment period (4-week follow up), subjects will complete a daily diary detailing symptoms and treatment details. Weekly from week 2 of RT until the end of treatment, study staff will assess the subject for radiation dermatitis by recording the RTOG for Radiation-Induced Acute Skin Toxicity scores and taking photographs. The same evaluation will be performed at the follow up visit after treatment. Subjects will complete the Dermatology Life Quality Index at each visit.

Inclusion Criteria:

Subjects must meet all of the following criteria:

- 1. Age ≥ 18
- 2. Female
- 3. Diagnosis of early stage (stage 0-2) breast cancer and scheduled to receive 4-6 weeks of fractionated radiation therapy as part of breast conserving therapy following lumpectomy

Exclusion Criteria:

Version: 00 03-01-2018

Effective Date:

Name of Company:Name of Product:Type of Study:KeraNetics, LLCKeraStat® CreamClinical Proof of Concept

To participate in the study, subjects must not meet any of the following criteria:

- 1. Previous radiation therapy to the area to be treated with radiation therapy
- 2. Receiving palliative radiation therapy
- 3. Low dose radiation protocol
- 4. Unhealed or infected surgical sites in the irradiation area
- 5. Patients undergoing cytotoxic chemotherapy or concurrent Herceptin as part of overall treatment plan (tamoxifen/aromatase inhibitor allowed)
- 6. Use of oral corticosteroids or topical corticosteroids in the irradiation area
- 7. Subjects with an autoimmune disease affecting the skin (e.g., scleroderma, systemic lupus erythematosus, psoriasis) are excluded. A history of other autoimmune disease that does not have direct skin involvement (e.g. rheumatoid arthritis, inflammatory bowel disease, multiple sclerosis) does not exclude participation on the study unless the subject requires active treatment with systemic steroids, immune suppression or biologic agents, or systemic chemotherapeutic agents (methotrexate or cyclophosphamide).

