- 8. Skin disease in target irradiation area
- 9. Known allergy to the standard of care or any of the ingredients in KeraStat Cream

Test Product(s), Dose, and Mode of Administration:

Investigational: KeraStat® Cream should be applied topically to the irradiation area and 1cm beyond the border of the affected area twice daily. Expel the cream from the tube. Smooth the cream over the target area to cover with a thin layer; do not rub the cream in.

Control: The standard skin care product should be applied topically to the irradiation area and 1cm beyond the border of the affected area twice daily. Smooth the product over the target area to cover with a thin layer; do not rub the product in.

Duration of Treatment:

The length of study participation for a subject is about 8-12 weeks.

Concomitant Medication Restrictions:

Chemotherapy, steroids

Criteria for Evaluation:

Effectiveness Evaluation:

Primary

- Safety and tolerability will be evaluated throughout the study utilizing patient reported outcomes
- Adverse events will be recorded throughout the study.

Secondary

- Maximum severity of radiation dermatitis as assessed by the RTOG Criteria for Radiation-Induced Acute Skin Toxicity.
- Number of subjects with Grade I radiation dermatitis
- Number of subjects with Grade II radiation dermatitis
- Number of subjects with moist desquamation present
- Change from baseline in the Dermatology Life Quality Index

Statistical Methods:

Feasibility:

Feasibility will be determined based on the average number of applications per week for a participant. Participants who average at least 10 applications per week will be classified as compliant. A 95% confidence interval will be calculated for the observed compliance rate. Along with the compliance rate, the number of tubes of KeraStat Cream used and the estimated surface area (bra size used as a surrogate) to be covered for each participant will be used to evaluate the coverage.

Safety:

Version: 00 03-01-2018

Effective Date:

Name of Company:Name of Product:Type of Study:KeraNetics, LLCKeraStat® CreamClinical Proof of Concept

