6. INVESTIGATIONAL PLAN

6.1. Overall Study Design

This is a single site, between subject, open-label comparison pilot study to assess the feasibility and effectiveness of KeraStat Cream in managing RT skin toxicity. The length of study participation for a subject is 8-12 weeks depending on when a subject returns for her final follow-up evaluation. The Study Design Schematic is shown below in Figure 1 with the Acceptable Study Windows in Table 2.

Sufficient subjects will be screened such that 24 total subjects will complete the study. Patient compliance is expected to be good, so a target recruitment of 26 subjects is desired.

Once a RT patient is determined to be a candidate for inclusion in this study, they may be approached for consent to participate. A total of 26 breast cancer patients scheduled to receive RT will be recruited and consented.

RT will begin 4 to 10 weeks after surgery; the targeted volume will be the ipsilateral breast with or without regional lymph nodes. Once the patient has consented to participate in the study, their baseline pre-RT assessments can be completed during the radiation treatment-planning process.

Patients are generally treated with RT Monday through Friday, with weekends and holidays off, for approximately 4 to 6 weeks. Patients will be provided with KeraStat Skin Cream for application as often as needed but at least twice daily, morning and evening.

During the course of treatment, the patient sees the radiation oncologist weekly in clinic to review the patient's treatment course, monitor the skin's appearance after application of KeraStat Skin Cream or standard of care, and answer questions. Breaks in the treatment schedule should be avoided whenever possible, but breaks necessitated by RT skin toxicity or for other reasons will be recorded. The radiation oncologist will see each patient in follow-up 4-8 weeks after completing RT to assess the patient for RT-induced skin and other toxicities that may have occurred.

Version: 00

Effective Date: 03-01-2018

Figure 1: Study Design Schematic

Table 2: Acceptable Study Windows

Visit	Day Visit	Acceptable Visit Window
Screening (Visit 1)	Day 1	None
Baseline (Visit 1)	Day 1	None
First evaluation (Visit 2)	RT Day 8	±2 days
Second evaluation (Visit 3)	RT Day 15	±2 days
Third evaluation (Visit 4)	RT Day 22	±2 days
Fourth evaluation (Visit 5)	RT Day 29	±2 days
Fifth evaluation (Visit 6)	RT Day 36	±2 days
Final evaluation (Visit 7)	Post RT Day 30	±14 days

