6.5. Study Procedures

6.5.1. Visit 1

After obtaining consent, ensuring the subject meets study inclusion/exclusion criteria, and randomizing the subject, study personnel will photograph the site to be irradiated. Study personnel will collect vital signs. Subjects will complete the Dermatology Life Quality Index. Study personnel will provide KeraStat Cream to subjects randomized to receive KeraStat Cream. Subjects randomized to standard of care will follow the instructions of their radiation oncologist. Study personnel will provide subjects with a daily diary form where subjects will note symptoms or treatment details of concern.

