11.3. Quality of Life

Subject quality of life will be measured using the Dermatology Life Quality Index. Subjects will complete the index at each visit. Quality of care will also be assessed qualitatively through examination of daily diary notes.

Version: 00

Effective Date:

03-01-2018

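### Section 12.1 tests DLQI score unadjusted and at no named visit, while the synopsis lists change from baseline; ANCOVA at one named visit, with the Visit 1 DLQI taken before the arm is disclosed, serves either reading

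*Combined protocol and SAP*

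**What the plan says.** Section 12.1 states that, once group summaries are done, "a t-test will be used to compare the two treatment groups for the effectiveness outcomes of DLQI score and RTOG score". No visit is named and no baseline term is mentioned. Section 12.2 and the effectiveness paragraph of the synopsis also speak of the score. The secondary criteria in the synopsis instead list "Change from baseline in the Dermatology Life Quality Index", again with no visit.

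Section 11.3 says "Subjects will complete the index at each visit". Table 2 in section 6.1 has Visit 1, five weekly evaluations and a final evaluation, so a subject can have up to six scores after baseline.

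On Visit 1, section 6.5.1 reads: "After obtaining consent, ensuring the subject meets study inclusion/exclusion criteria, and randomizing the subject, study personnel will photograph the site to be irradiated". Vital signs and the DLQI come next, and the cream is handed out after that. The synopsis keeps the same order: the sentence on randomisation is followed by "A physical exam and photograph of the area to be irradiated will be obtained, and subjects will complete the Dermatology Life Quality Index". The synopsis also states "This is a randomized, open label study".

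Section 12.2 gives 12 subjects per group and 80% power for a difference of 1.2 SD. One primary objective in the synopsis is "Collect data for designing a larger future trial evaluating KeraStat Cream".

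**The concern.** The endpoint list and the test do not name the same variable, and neither names a time. Two analysts following this text could run a t-test on a follow-up score or on its change from Visit 1, at any of up to six visits, and both could say they followed the plan. The two variables generally have different variances, so the same raw difference is detected with different power.

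The plan also collects a baseline DLQI that a t-test on the score does not use. ANCOVA uses it, and gives the same arm effect whether the outcome is called score or change.

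The second part concerns the quality of that baseline. If a subject in an open-label study knows her arm when she fills in the Visit 1 questionnaire, her answers may depend on it. Any analysis that uses the baseline, including the listed change endpoint, would then carry that shift into the estimated effect.

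**Working it through.** **Inputs.** From section 12.2: 12 per arm, difference 1.2 SD, power 80%. Assumed, because the documents do not give them: two-sided alpha 0.05; equal SDs at baseline and follow-up; baseline to follow-up correlation r = 0, 0.3, 0.5, 0.7; one visit; true difference 1.2 SDs of the follow-up score.

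**1. The plan's own figure.** Two-sample t-test on the score, 22 df, critical value 2.074. Noncentrality = 1.2 / √(1/12 + 1/12) = 1.2 / 0.408 = 2.94. Power is 0.802, and the detectable difference at 80% power is 1.197 SD. The stated figure reproduces, in the SD of whichever variable is tested.

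**2. t-test on change.** The SD of change is √(2(1−r)) follow-up SDs. The standardised difference is 1.2 / √(2(1−r)) = 0.85, 1.01, 1.20, 1.55 for the four values of r.

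**3. ANCOVA on arm and Visit 1 DLQI.** The residual variance is (1−r²), with 21 df. Chance baseline imbalance inflates the variance of the arm effect by an expected factor of 1 + 1/(24−4) = 1.05. The standardised difference is 1.2 / √(1.05(1−r²)) = 1.17, 1.23, 1.35, 1.64. Simulation (100,000 runs per r, bivariate normal) gives 0.784, 0.819, 0.883, 0.968.

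| Power | r = 0 | 0.3 | 0.5 | 0.7 |
|---|---|---|---|---|
| Score t-test | 0.80 | 0.80 | 0.80 | 0.80 |
| Change t-test | 0.51 | 0.66 | 0.80 | 0.95 |
| ANCOVA | 0.78 | 0.82 | 0.88 | 0.97 |

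ANCOVA breaks even with the score t-test where 1.05(1−r²) is about 1, that is r = √(1 − 1/1.05) = 0.22. Simulation agrees: 0.798 at r = 0.20 and 0.802 at r = 0.22.

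**4. Where the loss at r = 0 comes from.** Going from 22 to 21 df alone moves power from 0.802 to 0.800. The rest of the fall to 0.78 is chance baseline imbalance. The CI widens by √1.05 × 2.080/2.074 = 1.03, about 3%.

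**5. Sensitivity.** If the baseline SD is half the follow-up SD, the change t-test gives 0.71, 0.82, 0.90, 0.97 and ANCOVA 0.78, 0.82, 0.88, 0.97, so ANCOVA's advantage over change disappears for r of 0.3 or more. With a floored, skewed baseline at the same r, ANCOVA gives 0.78, 0.82, 0.89, 0.97. In all these cases ANCOVA is at most about 2 points below the better t-test.

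**6. Same effect for score or change.** If Y = a + τ·arm + bX, then Y − X = a + τ·arm + (b−1)X. The arm coefficient τ is identical.

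**7. Order of steps at Visit 1.** Suppose knowing the arm shifts the Visit 1 DLQI by 0.3 SD in one arm (assumed), with no true effect. The size of the bias is 0 for the score t-test, r × 0.3 for ANCOVA and 0.3 for change.

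| r | 0.3 | 0.5 | 0.7 |
|---|---|---|---|
| Bias, ANCOVA (SD) | 0.09 | 0.15 | 0.21 |
| Bias, change (SD) | 0.30 | 0.30 | 0.30 |
| Type I error, score | 0.05 | 0.05 | 0.05 |
| Type I error, ANCOVA | 0.056 | 0.066 | 0.103 |
| Type I error, change | 0.092 | 0.107 | 0.149 |

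**8. A visit that everyone reaches.** A four-week Monday-to-Friday course that starts on a Monday without breaks ends on day 1 + 21 + 4 = 26. Of the weekly evaluations in Table 2, RT Days 8, 15 and 22 fall inside it; 29 and 36 do not. RT Day 22 and the final evaluation are therefore the natural candidates.

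**The case against.** The strongest reply is that ANCOVA is a preference. Both t-tests are valid under randomisation, r is unknown, and subjects enter before radiotherapy without skin disease or unhealed sites in the field, so the baseline may vary little and r may be low. This stands in part. The gain is conditional, and the skewed-baseline check holds r fixed, so it does not show that a floor leaves r intact. It does not answer the mismatch between endpoint and test, or the missing visit, which need repair under any method.

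A reader might infer that the test chosen here fixes the variance for the next trial. The next trial's N relative to a score t-test would indeed be 2(1−r) = 2.0, 1.4, 1.0, 0.6 times for change and 1−r² = 1.0, 0.91, 0.75, 0.51 times for ANCOVA. But the SDs and the correlation can be computed from the collected data whichever test is run, so these ratios describe a later choice and not damage done by section 12.1. The pilot will also estimate r poorly: an observed 0.5 with 24 subjects has a 95% interval of about 0.12 to 0.75.

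A reader might infer that the baseline is answered with the arm known. The documents give only the order of steps; they do not say when the subject learns her arm, and the cream is handed out after the questionnaire. The exposure is possible, not shown, and the 0.3 SD shift is an assumption. If it does occur, ANCOVA is worse than the unadjusted score t-test, so the repair must depend on the order of steps.

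A reader might also infer testing at all six visits, with an inflated false-positive rate. No such plan is stated.

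The same sentence in 12.1 leaves the RTOG score without a visit. That is true, but it is a separate point.

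**Conclusion.** The point holds as a cheap improvement, not as an error in the plan. Section 12.1 leaves the DLQI variable and visit open, and the synopsis endpoint differs from the tested variable. The documents do not support calling either t-test invalid or the 80% power wrong.

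With 12 per arm and equal SDs, reading the endpoint as change puts power for 1.2 follow-up SDs anywhere from 0.51 to 0.95 over r = 0 to 0.7. ANCOVA stays between 0.78 and 0.97 and settles both readings with one arm effect. There is no gain over the score t-test below r of about 0.2, and little or none over change if the baseline SD is much the smaller. The Visit 1 order is a possible source of bias that can be removed at no cost in data.

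The stakes are modest: DLQI is a secondary outcome in a pilot, no decision rests on it, and the next trial's variances remain available in any case.

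**What to change.** 1. **Section 6.5.1 and the synopsis:** have the Visit 1 DLQI completed before the assignment is made or disclosed.
2. **Section 12.1:** replace the DLQI t-test with a comparison at one pre-named visit that all subjects reach, by ANCOVA on arm and Visit 1 DLQI, reporting the adjusted difference with its 95% CI. RT Day 22 and the final evaluation are examples; the choice is the sponsor's. Summarise the other visits by arm. Report the SDs of both scores and their correlation for sizing the next trial. If step 1 cannot be assured, keep the unadjusted t-test on the named-visit score as the main comparison and give ANCOVA as supportive.
3. **Section 12.3:** it now puts all information from withdrawn subjects into the analyses, which a single-visit comparison cannot do. State that a subject with a score at the named visit enters the comparison even if she withdraws later, and that all other completed assessments enter the summaries.
4. **Section 12.2:** keep 1.2 SD and describe it as the unadjusted two-sample calculation.

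Cost: wording in four places and one reordered step, with no new data. If r is near 0, about 2 power points are lost and the CI is about 3% wider, mostly from chance baseline imbalance. Subjects who withdraw before the named visit are summarised but not compared.
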